#### 2.2.3 Rehabilitation programmes

Existing rehabilitation programmes

Rehabilitation programmes currently run in two physiotherapy departments of The Pennine Acute Hospitals NHS Trust. These locations deliver similar programmes that consist of 3-3.5 hour sessions over 5/6 consecutive weeks. The programmes are delivered by healthcare professionals (physiotherapists and psychological wellbeing practitioners). The current programmes involve graded exercise, relaxation and discussion into coping strategies such as promoting healthy sleep behaviours, medication, balancing 'choice' and 'demand' activities and activity pacing. Pacing is currently instructed during one session of the programme and these instructions are not standardised by

any specific framework. Pacing is referred to informally throughout the duration of the programme, for example, to assist patients' approach to graded exercise.

## Activity pacing framework standardised programme

The newly developed activity pacing framework will be used to structure and standardise the instructions of pacing across the 5/6-week's rehabilitation programmes. The pacing framework clarifies the conceptual model of pacing on which the instructions are based. This pacing framework is underpinned by the operant approach of pacing rather than adaptive pacing therapy/energy conservation. The framework details the aims of pacing, different facets of pacing and contains tools/exemplars for healthcare professionals to assist their instruction of pacing to patients (see Appendices 4 and 5 for the Activity Pacing Framework 'Theory and Overview' and 'Appendices and Teaching Guide' respectively). In comparison to the existing rehabilitation programmes, pacing will be instructed on one session and revisited the following week. During this 1-week period, patients will be asked to complete an activity diary in order to discuss their activity patterns the following week. Pacing will be referenced throughout the programme in relation to the other coping strategies, since pacing principles apply to the use of relaxation and healthy sleeping behaviours. This is also advised in the activity pacing framework/appendices. Pacing is rarely implemented in isolation and so it will be explored in the current study as part of a programme alongside other coping strategies. This approach is similar to other pacing studies (Nielson and Jensen, 2004; Cane et al., 2013).

The implementation of a standardised and evidence-based framework is considered to be a service development. The modifications will therefore be applied to all programmes across the different locations and all patients will attend the same programmes whether they choose to participate in the study or not. There is no harm envisaged through using the framework, rather, the framework aims to develop the current service by promoting more detailed and standardised information on activity pacing.

The healthcare professionals who usually deliver the programmes (n=8-10) will receive training on using the framework during a half-day session and they will also have regular contact with the Chief Investigator (face-to-face, or via the phone/email). Healthcare professionals will be advised that they can ask the Chief Investigator questions about the pacing framework at any time. The training will involve instructions on the different types of pacing and the model of pacing contained within the activity pacing framework. Healthcare professionals will be trained on the different facets of pacing and how these can be adapted and tailored to individuals according to their current activity behaviours and goals. The training will also involve practical issues around recruitment, administering consent forms/questionnaire booklets, and with regards to answering patients' questions regarding the research study.

No threats to patients' health are anticipated through their participation, since patients routinely attend rehabilitation programmes for chronic pain/fatigue within these physiotherapy departments. Pacing currently features in the rehabilitation programmes, however, it is not currently advised based on an evidence-based framework, nor is it standardised across the healthcare professionals delivering the programmes.

This study will not include a control group, since it aims to explore the feasibility of the protocol to assess the pacing framework in clinical settings, and not compare the effects of the programme against those not involved in a programme underpinned by the pacing framework. This is in keeping with the exploratory phase of the MRC framework for complex interventions.

## 2.2.3 Data collection methods

#### 2.2.3.1 Outcome evaluation

Participants will be invited to sign the study consent form and complete the pretreatment questionnaire booklet (T1). The T1 questionnaire booklet will be sent via the post one week before attending the programme (T1\_Post). Those patients who did not sign the consent form and complete the T1 questionnaire booklet at home will also have the opportunity to do that during the break-time on week 1 of the programme (T1 Dept). Those patients not consenting to the study will complete the usual department-required measures that are collected during Week 1 and 6 of the programme. The department-required measures are positioned at the front of the questionnaire booklet with a 'tear away' section for those questionnaires needed only for the research study.

Patients will be invited to complete the post-treatment questionnaire booklet (T2) during the break-time of the last week of the programme in the physiotherapy department. The 3-months follow-up questionnaire booklet (T3) will be administered via the post. If no response is made to the follow-up questionnaire within two weeks, patients may be called to clarify any questions they have regarding the study, and to clarify whether they wish to continue to participate in the study through returning the T3 booklet. Alternatively, patients may be invited to answer some questions from the questionnaire booklet over the telephone. If patients consent to this, the priority questionnaires from the booklet will be asked, for example, regarding pain, pacing and health status. Prior to full data collection, the questionnaires have been piloted on three individuals not involved in the study to check the suitability of the layout, and the time and burden of completion.

The T1 questionnaire booklet will contain demographic questions regarding age, gender, condition(s)/main condition, duration of condition, ethnicity, living situation (living alone/with others) and employment status; and the activity pacing questionnaire will be used as the measure of pacing. The questionnaire booklet will include validated measures of symptoms frequently reported by patients: pain, fatigue, anxiety and depression. The questionnaire will also assess self-efficacy as a driver for behavioural change, avoidance as a common behaviour presenting with this patient group, physical/mental function and health status. Many of the above constructs are important components of the HAPA behavioural model.

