A minimum recruitment rate of 50% is estimated since patients will be advised that their participation involves only the completion of a questionnaire booklet at the beginning and end of treatment and at 3-months follow-up after finishing the programme. It is current practice in the physiotherapy departments for patients to complete questionnaire booklets at the beginning and end of the rehabilitation programmes, and so participating in the study will be an extension of this usual practice. Patients will be advised that their personal data will remain strictly confidential and anonymised during data analysis and any publication of the results. However, patients will have the option of not consenting, leading to the conservative estimate of a 50% recruitment rate.

A completion rate of the rehabilitation programme of approximately 60% is expected based on current rates of the programmes running in the physiotherapy departments. The return rate of the 3-months follow-up questionnaire booklet is envisaged to be 50% based on recruitment rates into the previous APQ study (Antcliff et al., 2015). The estimated combined retention rate is 30%. Therefore, to achieve a sample size of approximately 50 participants at 3-months follow-up who have both completed their rehabilitation programme and returned their follow-up questionnaires, 340 patients will be invited to participate. This number is feasible based on the approximate 380

patients referred to the programmes each year. The criteria for patients to be referred to the rehabilitation programmes is similar to that of the inclusion criteria for the study, therefore, the majority of the 380 patients referred into the group will be eligible to participate in the study. If more than 50 participants respond to the 3-month's follow up questionnaire, these data will be included to maximise data analyses.

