Recruitment will occur from physiotherapy departments at two locations in The Pennine Acute Hospitals NHS Trust. Fairfield General Hospital runs approximately fourteen 6-week's programmes each year with a maximum of 12 participants per group. Recruitment will launch at this site first and recruit over a 15 month period (18 groups with 12 patients: n=216 invited to participate). Following the study set-up at Fairfield General Hospital, recruitment is envisaged to occur over a 12 month period from approximately fourteen 5/6-week's rehabilitation programmes at North Manchester General Hospital with a maximum of 12 participants each group (14 groups with 12 patients: n=168 invited to participate). Recruitment will occur over a 15-month period and data collection will occur over 20 months to allow for the 3-month follow-up questionnaire to be administered following the completion of the 5/6-week's programmes. To increase the follow-up return rate at 3-months, prepaid addressed envelopes will be provided and reminder phone calls will be made. (See Figure 2. Timetable of the study).

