#### 9.) EuroQol (EQ-5D-5L)

The EuroQol (EQ-5D-5L) is a generic measure of health status that is widely used to assess both clinical and economic efficacy; and to compare health status across diseases (Brooks, 1996; Devlin and Brooks, 2017). The EQ-5D-5L measures health related quality of life via dimensions of mobility, self-care, usual activities, pain and anxiety/depression (Devlin and Brooks, 2017). The EQ-5D-5L was developed to reduce the possible ceiling effects of the EQ-5D-3L which contained only three levels of answers to each question (Devlin and Brooks, 2017).

The T2 and T3 booklets will contain the same questionnaires, except without the demographic questions. The T2 booklet will additionally contain two 11-point numerical rating scales (0-10) regarding satisfaction of the programme content and length. The T2 questionnaire booklet will also include a question inviting participants to indicate whether they would be interested in participating in the acceptability interviews (see Appendices 6, 7, 8 and 9 for the T1\_Post, T1\_Dept, T2 and T3 questionnaire booklets respectively; and Appendix 10 for the covering letter for T3).

Participants will be asked to complete a 1-week activity diary after activity pacing is introduced in the rehabilitation programme. The diaries will be used the following week to assess patients' patterns of behaviour, and to set goals towards pacing that are individualised. (See Appendix 5: Activity Pacing Framework 'Appendices and Teaching Guide' for the activity diaries.)

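### One collection route is described for T2, the break of the last session, so T1-T2 change and satisfaction would probably describe last-session attenders; posting T2 to absentees is a cheap improvement

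*Combined protocol and SAP*

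**What the plan says.** Section 2.2.3.1 (Outcome evaluation) sets out how the three booklets are collected.

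- **T1** is posted a week before the programme. Anyone who has not completed it can do so in the break of the first session.
- **T2** has one described route: patients are invited to "complete the post-treatment questionnaire booklet (T2) during the break-time of the last week of the programme in the physiotherapy department".
- **T3** is remote: "The 3-months follow-up questionnaire booklet (T3) will be administered via the post". Non-response has its own provision: "If no response is made to the follow-up questionnaire within two weeks, patients may be called", and priority questionnaires may be answered by telephone. Section 2.2.1.3 adds, for the 3-month return, that prepaid "envelopes will be provided and reminder phone calls will be made".

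On content: "The T2 and T3 booklets will contain the same questionnaires, except without the demographic questions". However, "The T2 booklet will additionally contain two 11-point numerical rating scales (0-10) regarding satisfaction of the programme content and length", and T3 is not said to carry these scales.

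On numbers, section 2.2.1.3 estimates 50% recruitment and 50% return at T3. It also states: "A completion rate of the rehabilitation programme of approximately 60% is expected". The target is about 50 participants "who have both completed their rehabilitation programme and returned their follow-up questionnaires, 340 patients will be invited to participate".

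Section 2.2.4 compares completers with non-completers on demographics. It does not say how a missing T2 is handled.

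**The concern.** T2 is tied to physical presence at one session of a programme that about four in ten people are expected not to complete. The other two time points can be reached from home.

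The study is meant to assess attrition, the protocol and the outcome measures (section 1.4.1), and to supply means, standard deviations and differences for a later trial (sections 2.2.1.2 and 2.2.4). Section 4.2 says that trial will again collect outcomes before treatment, after treatment and at 3 months, with a control arm. The post-treatment time point will therefore be reused.

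Under the plan as written, the later trial would inherit a T1-T2 change and standard deviation from people present at the end. It would have no direct figure for how many leavers return a post-treatment booklet. The satisfaction ratings, which section 2.2.3.2 uses for process evaluation, would have the same restriction.

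**Working it through.** **Inputs from section 2.2.1.3:** 340 invited, 50% recruited, 60% programme completion, 50% T3 return, and a target of about 50 completers with T3.

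**The plan's own figures**
- Combined retention: 0.60 × 0.50 = 0.30, as stated.
- Number to invite: 50 / (0.50 × 0.60 × 0.50) = 333.3, so 334. The stated 340 is consistent with this.
- Forward: 340 × 0.50 = 170 consenters; 170 × 0.60 = 102 completers; 102 × 0.50 = 51 with T3.

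**Consenters without T2**

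Share missing = 1 − (proportion present at the last session × proportion of those who fill in T2).

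The base case takes completion as presence at the last session and assumes that everyone present fills in T2: 1 − 0.60 × 1 = 0.40, or 170 − 102 = 68 people.

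The protocol does not define completion in this way and states no T2 return rate. The alternatives below are my assumptions:

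| Assumption | With T2 | Without T2 |
|---|---|---|
| 70% present, all fill in T2 | 119 | 51 (30%) |
| 60% complete, and 25% of non-completers also attend the last session: 0.60 + 0.40 × 0.25 = 0.70 | 119 | 51 (30%) |
| 60% present, all fill in T2 | 102 | 68 (40%) |
| 50% present, all fill in T2 | 85 | 85 (50%) |
| 60% present, 80% fill in T2: 0.60 × 0.80 = 0.48 | about 82 | about 88 (52%) |

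**What a posted T2 could add (base case, assumed 20% to 50% return)**
- Extra booklets: 68 × 0.20 = 13.6 to 68 × 0.50 = 34.
- Coverage: 115.6 to 136 of 170, or 68% to 80%, against 60% without posting.
- 95% half-width for the absentee return rate, n = 68: 1.96 × √(0.2 × 0.8 / 68) = 0.095; 1.96 × √(0.5 × 0.5 / 68) = 0.119. That is about 10 to 12 percentage points.

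**Timing**

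Recruitment closes at 15.0 months. Six weeks later is about 16.4 months, and a two-week window ends at about 16.8 months. Both fall in month 17, the last T2 month in Figure 2. T3 for the same groups falls at about 16.4 + 3 = 19.4 months, in month 20.

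**The case against.** The strongest reply is that the gap is one of silence and its consequences are limited. Several parts of that reply stand.

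- **No prohibition.** A reader might infer that T2 cannot be completed any other way. The text only says that patients are invited to complete it at the last session. It does not bar a later or posted booklet, and the appendices are not available here. What can be said is that no other route is described.
- **The 40% is an inference.** Completion is undefined, and 60% is the current rate of the service rather than a rate observed in consenters.
- **Leavers are not lost.** T3 is not stated to be limited to completers and carries the same outcome questionnaires. It can show leavers' later outcomes, and their T3 return is a usable proxy for postal return of T2. Section 2.3.1.3 allows interviews with non-completers who returned T1 and attended at least the first two sessions, without a T2. Section 2.4 lists programme attrition separately from booklet completion, so T2 return among attenders can be worked out.
- **The target is unaffected.** It counts completers with T3 (51 expected), and about 102 T2 booklets are expected.
- **The remedy has limits.** Late postal returns mix setting and timing. A rating of content and length from someone who attended no session means little.

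What the reply does not supply is absentees' scores at programme end, their satisfaction ratings, or a direct estimate of their T2 return. Section 2.3.1.3 shows that non-completers were foreseen, since it adds a separate invitation route for interviewees who would otherwise be identified through T2. No similar step is described for T2 itself.

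**Conclusion.** The point holds as a moderate weakness with a cheap remedy. The protocol describes one T2 route, and on its own rates about 68 of 170 consenters (40%) would have no T2. The figure assumes that completion approximates last-session attendance and that all attenders respond; other assumptions give 30% to 52%. T1-T2 change, its standard deviation and the satisfaction ratings should be read as last-session-attender estimates unless the plan changes.

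A reader might go further and infer that T1-T2 change or satisfaction will look too favourable. The documents give no basis for the direction or size of any bias. Nor do they support saying that leavers' outcomes are unobtainable or that the study's sample-size target is at risk.

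**What to change.** 1. Post T2, with a prepaid envelope and one reminder call, to consented participants who have not withdrawn and were absent from the last session. Send it at the scheduled programme end, with a short return window, for example about two weeks, matching the interval already used before T3 calls.
2. Record the date and place of completion and the number of sessions attended.
3. Report T1-T2 change overall and separately for last-session attenders and absentees, and report the T2 return rate among absentees.
4. Summarise satisfaction with content and length only for those who attended at least one session.
5. If postal T2 is not adopted, label T1-T2 change and satisfaction as last-session-attender estimates.

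**Cost.** A protocol amendment and about 70 mailings and calls, using the T3 procedure and contact details already held (section 3.5). No new staff should be needed, and a two-week window stays within the T2 period in Figure 2. T2 would be of mixed setting and timing, with absentees' interval from T1 up to about two weeks longer; the recorded date and place make this visible but do not remove it. The extra booklet might reduce T3 return among leavers. A fall of an assumed 5 to 10 percentage points would lose 68 × 0.05 = 3.4 to 68 × 0.10 = 6.8 booklets, about 3 to 7, mostly outside the completer-based target.

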#### 1. Activity Pacing Questionnaire-28

The Activity Pacing Questionnaire-26 (APQ-26) has been initially validated among a sample of patients with chronic pain/fatigue. Factor analysis identified five themes of pacing contained within the APQ-26. These five

themes demonstrated satisfactory internal consistency (Cronbach's alpha=0.72-0.92; test-retest reliability intra-class correlation coefficient=0.50-0.78, p≤0.001) and construct validity against validated psychometric measures (Antcliff et al., 2015).

The APQ-26 has been modified for the purpose of this study with the addition of two items to correspond to important aspects of pacing that emerged during Stages I and II of the study and also appear in the literature regarding pacing. These two items involve finding a baseline of activities and being flexible. The APQ-28 reflects the content of the activity pacing framework.

## 2.) 11-point numerical rating scale

Two 11-point Numerical Rating Scales (NRS) will assess current pain and usual pain, where 0='no pain' and 10='worst possible pain' (Jensen et al., 1994). The 11-point NRS are frequently used and have been found to have ease of completion, responsiveness and sensitivity to change in symptoms (Ferreira-Valente et al., 2011).

#### 3.) Patient Health Questionnaire

The Patient Health Questionnaire (PHQ-9) contains nine items that screen for and measure the severity of depression in the clinical setting. Items are developed based on the Diagnostic and Statistical Manual of Mental Disorders 4th Edition (DSM-IV) (Kroenke et al., 2001). Each item is rated on a 4-point Likert scale (0-3) with a 2-week recall period. Scores of 1-4=no depression, 5-9=mild depression, 10-14=moderate depression and 15-19=severe depression (Kroenke et al., 2001). The PHQ-9 has demonstrated good internal consistency (Cronbach's alpha=0.86-0.89), test-retest reliability (0.84-0.95) and construct validity against other measures of depression (Smarr and Keefer, 2011; Kroenke et al., 2001; Cameron et al., 2008).

#### 4.) Generalised Anxiety Disorder Assessment

The Generalised Anxiety Disorder Assessment (GAD-7) contains seven items that screen for and measure the severity of anxiety in the clinical setting. The items are based on the Diagnostic and Statistical Manual of Mental Disorders

4th Edition (DSM-IV) (Spitzer et al., 2006). Items are rated on a 4-point Likert scale (0-3) over a 2-week recall period and cut-off scores of 5=mild anxiety, 10=moderate anxiety and 15=severe anxiety (Spitzer et al., 2006). The GAD-7 has demonstrated good reliability (Cronbach's alpha=0.89-0.92), test-retest reliability (Intraclass correlation=0.83) and construct validity against other measures of anxiety (Spitzer et al., 2006; Lowe et al., 2008).

#### 5.) Pain Self-Efficacy Questionnaire

The Pain Self-Efficacy Questionnaire (PSEQ) contains 10 items that assess a persons' confidence in their ability to do things despite their pain. Each item is rated on a scale from 0-6 where 0=not at all confident and 6=completely confident. Cut-off scores of PSEQ≥40 are considered high and PSEQ≤16 are considered low (Nicholas, 2007). The PSEQ has been found to have high internal consistency (Cronbach's alpha=0.92), test-retest reliability (r=0.73, p<0.001) and construct validity against other measures of self-efficacy and other constructs (Nicholas, 2007; Miles et al., 2011).

## 6.) Chalder Fatigue Questionnaire

The Chalder Fatigue Questionnaire (CFQ) contains two subscales: physical fatigue (seven items) and mental fatigue (four items). All items are rated on 4-point Likert scale (0='better than usual', 3='much worse than usual') (Chalder et al., 1993). The scale has demonstrated good reliability and concurrent validity with regards to sensitivity and specificity (Chalder et al., 1993).

